10.8. Subjective time to ON

The time to ON is defined as time from first dosing to the first onset of ON status. Subjects without onset of ON status will be censored at the last assessment time. The analysis method for time to ON endpoint will be the same as that for time to response endpoint. Survival analysis will be used to analyze the time to ON. The analysis of time to ON is based on the survivor function, which is the probability to survive or, more generally, to stay event-free beyond a certain point in time. The survival function will be estimated by the Kaplan-Meier method. The survival function will be summarized for 25th percentile, median, and 75th percentile and their 95% confidence intervals. The plot of Kaplan-Meier estimates for the treatment groups will be presented. The y-axis of Kaplan-Meier estimates will be plotted as cumulative event (response) rate (i.e. one minus survival rate).

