Treatment Groups:	
Subjects will receive one of the following treatments:
 
All subjects in Cohorts 1, 2 and 3 will receive oral benserazide hydrochloride (benserazide) 25 mg at 60 ± 5 minutes prior to INP103 or placebo dosing and time recorded. Cohorts 1, 2 and 3 will comprise eight subjects total; six subjects in receipt of INP103 (L-dopa via I231 POD Device) and two subjects placebo (via I231 POD Device).
 
Cohort 4 will NOT receive oral benserazide. Cohort 4 will comprise of eight subjects; six subjects in receipt of INP103 (L-dopa with carbidopa via I231 POD Device) and two subjects placebo (via I231 POD Device). At the discretion of the Sponsor, depending on rate of recruitment, cohort 4 may be over enrolled with a total of up to 12 subjects using the 3:1 randomization scheme.
 
Cohort 1 (INP103 35 mg L-dopa total or placebo as one spray to one nostril): Each subject in this cohort will receive one dose of INP103 or placebo delivered by one actuation of the device.
 
Cohort 2 (INP103 70 mg L-dopa total or placebo as one spray to each nostril): Each subject in this cohort will receive one dose of INP103 or placebo delivered by two actuations of the device.
 
Cohort 3 (INP103 140 mg L-dopa total or placebo as two sprays to each nostril): Each subject in this cohort will receive one dose of INP103 or placebo delivered by four actuations of the device.
 
Cohort 4 (INP103 70 mg L-dopa/7.0 mg carbidopa total or placebo as one spray to each nostril): Each subject in this cohort will receive one dose of INP103 or placebo delivered by two actuations of the device, one to each nostril.
 
At 120 minutes post study dosing, subjects should take their usual anti-OFF medication (e.g. Madopar rapid) if they have not returned to ON, and their usual morning dose of PD medications (e.g. their regular Madopar® or Sinemet® morning dose). Subjects will remain under observation for another 120 minutes before they can be allowed to leave (health status permitting).
 
Escalation to Cohorts 2 and 3 may only commence after review and approval of safety data by a SMC (see Study Design, above) of Cohorts 1 and 2 respectively. There will be no SMC meeting between Cohorts 3 and 4 if there are no safety concerns raised by the SMC meetings occurring after Cohorts 1 and 2, since the dose of L-dopa and DCI in Cohort 4 is less than Cohort 3. However, all usual safety monitoring will remain in place.

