7.4.3. After Dosing

The subjects will remain in the study clinic post-dose through to the completion of all scheduled post-dose procedures 240 minutes after dosing.

The subject's usual rescue (anti-OFF [e.g. Madopar rapid]) medication will be permitted from 120 minutes post-dose (once all 120 minute assessments have been completed, but can precede ECG, physical examination and subject questionnaire) – if they are still OFF. In addition, subjects should take their regular anti PD medication (e.g. their regular morning Madopar dose) at 120 minutes post dosing whether or not they have returned to ON.

The following in-patient assessments will be performed after dosing:

1. Adverse Events (including overall dyskinesia rating) and concomitant medications will be continually monitored post-dose.
2. Vital signs will be measured at 30, 60 and 120 minutes post-dose. Blood pressure (supine and standing) and heart rate, respiratory rate and oral temperature (supine only) will be measured at all time points. Vital signs will be collected after MDS-UPDRS assessment (where both procedures are scheduled at the same time point) and will not be deemed protocol deviations if they occur outside the time window at each timepoint.
3. PK blood samples will be collected at 4, 9, 14, 29, (all + 1 minute) 44, 59, 89 and 119 (all \pm 2 minutes at each timepoint) minutes post-dose and will precede UPDRS assessments.
4. MDS-UPDRS III only at 15, 30, 45, 60, 90 and 120 minutes post-dose for Cohorts 1, 2 and 3) and 30, 60, 90, 120 minutes for Cohort 4 (\pm 2 minutes at each timepoint)
5. Investigator and subject self-assessment of ON/OFF at 30, 45, 60, 90, 120 and 240 minutes post-dose (\pm 10 minutes at each timepoint)
6. At 120 minutes, the subject's usual morning dose of all Parkinson's medications should be given following completion of assessments 1-5, regardless of ON/OFF state. In addition, if subject is still OFF, their usual OFF medication may be given (prior to completing assessments 7, 8 and 9).
7. Directed physical examination (including nasal inspection) will be performed at 120-180 minutes post-dose

8. 12-Lead ECG will be performed at 120-180 minutes post dose. In cases where vital signs are scheduled at the same time point, ECG will be completed in sequence with vital signs per the usual practice of the study sites.
9. Subject questionnaire will be completed as the last assessment from 120-180 minutes post-dose

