12.5. Pharmacodynamic Analysis

The changes from baseline in MDS-UPDRS Part III scores will be summarized by treatment groups and estimated using a Mixed Model for Repeated Measures (MMRM) with treatment group (INP103 35 mg, INP103 70 mg, INP103 140 mg, INP103 70mg with 7.0 mg carbidopa, or placebo), time point (15, 30, 45, 60, 90 or 120 minutes for INP103 and benserazide [C1, C2, C3] and 30, 60, 90, 120 minutes for INP103 and carbidopa [C4])) and the interaction between treatment group and time point as fixed factors. The baseline score will be included as a covariate. The focus will be on the estimation of changes within each treatment group. An unstructured covariance structure will be used for the MMRM. In case the model does not converge with the unstructured covariance structure, the heterogeneous compound symmetry (CSH) or heterogeneous Toeplitz structure (TOEPH) will be used instead. The denominator degrees of freedom will be computed using the Kenward-Roger method. The least square (LS) means, standard errors and two-sided 95% confidence intervals will be provided for changes within each treatment group. In addition, the differences between each treatment group and placebo will be estimated.

The cumulative proportion of responders will be summarized descriptively by treatment group and time point.

The endpoint related to time of response and time to ON will be evaluated with Kaplan-Meier methods. The figures of Kaplan-Meier estimate and summary statistics (25th percentile, median, and 75th percentile and their 95% confidence intervals) will be presented.

For subjects who received study drug administration and achieve response within 120 minutes post dosing, the duration of response will be summarized by treatment group. If the subject did not achieve response after 120 minutes post dosing, this subject will be regarded as censored and the duration of response will be treated as missing.

The AUC of MDS-UPDRS Part III scores from pre-dose to 15, 30, 45, 60, 90 and 120 minutes will be calculated as AUC_{0-15} , AUC_{0-30} , AUC_{0-45} , AUC_{0-60} , AUC_{0-90} and AUC_{0-120} (omitting AUC_{0-15} and AUC_{0-45} for Cohort 4). These AUC parameters will be summarized by treatment groups as well as analysed with an Analysis of Covariance (ANCOVA) model with treatment group as a fixed factor and baseline MDS-UPDRS Part III score as a covariate. The least square (LS) means, standard errors and two-

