3.2.2. Secondary Endpoints

1. PK profile of L-dopa for 120 minutes following dosing with INP103 (AUC_{0-2h}, C_{max} and T_{max}).
2. Motor function, evaluated as:
 - Change from baseline to 30 minutes post-dose in Movement Disorder Society Unified Parkinson's Disease Rating Scale (MDS-UPDRS) Part III score (primary motor function endpoint).

- Change from baseline to 15, 30, 45, 60, 90 and 120 minutes post-dose for Cohort 1 (C1), Cohort 2 (C2), Cohort 3 (C3) and change from baseline to 30, 60, 90, 120 minutes for Cohort 4 (C4), in MDS-UPDRS Part III score.
 - Cumulative proportion of responders by post-dose time point (15, 30, 45, 60, 90 and 120 minutes for C1, C2, C3 and change from baseline to 30, 60, 90, 120 minutes for C4), where response is defined as an improvement of 30% in MDS-UPDRS Part III score from baseline.
 - Time to response, where response is defined as an improvement of 30% in MDS-UPDRS Part III score from baseline.
 - Duration of response, where response is defined as an improvement of 30% in MDS-UPDRS Part III score from baseline
 - Area Under the Curve (AUC) of changes in MDS-UPDRS Part III scores from pre-dose to 15, 30, 45, 60, 90 and 120 minutes for C1, C2, C3 and change from baseline to 30, 60, 90, 120 minutes for C4
 - Maximum response in MDS-UPDRS Part III scores from pre-dose to 15, 30, 45, 60, 90 and 120 minutes for C1, C2, C3 and change from baseline to 30, 60, 90, 120 minutes for C4
 - Subjective time to ON, as evaluated by the Investigator and by subject self-assessment
3. The PK/PD_{yn} relationship of single doses of INP103 and motor function

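### SAP 10.8 puts no upper limit on time to ON, so a first ON at 240 minutes, after the usual Parkinson's medication planned at 120 minutes, counts as an event for INP103 or placebo

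*SAP*

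**What the plan says.** SAP 3.2.2 lists the endpoint as "Subjective time to ON, as evaluated by the Investigator and by subject self-assessment". SAP 10.8 defines it: "The time to ON is defined as time from first dosing to the first onset of ON status". The censoring rule follows: "Subjects without onset of ON status will be censored at the last assessment time". The analysis is Kaplan-Meier, with quartiles, their 95% confidence intervals and a plot of the cumulative event rate.

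Protocol 7.4.3 schedules "Investigator and subject self-assessment of ON/OFF at 30, 45, 60, 90, 120 and 240 minutes post-dose", with a window of plus or minus "10 minutes at each timepoint". The same list says that at 120 minutes the subject's usual morning Parkinson's "medications should be given following completion of assessments 1-5, regardless of ON/OFF state". Anti-OFF medication may be added for a subject still OFF. The synopsis (Treatment Groups) agrees: at 120 minutes "subjects should take their usual anti-OFF medication (e.g. Madopar rapid) if they have not returned to ON", together with the usual morning dose.

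Protocol 12.5 names Kaplan-Meier for time to ON and gives no time limit. In the same section, duration of response is summarised for subjects who "achieve response within 120 minutes post dosing".

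**The concern.** The only scheduled ON/OFF rating after 120 minutes follows treatment that is not under study and is planned for everyone. To be eligible, every subject had to respond to L-dopa medication at Visit 2. First ON at 240 minutes is therefore a pattern to expect in subjects who did not respond to INP103 or placebo. SAP 10.8 scores that pattern as an event for the randomised treatment.

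A group in which few subjects turn ON during the study-treatment period could thus show a finite median or 75th percentile where the honest entry is that it was not reached. Pooled placebo and any poorly responding dose group are the most exposed.

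**Working it through.** The documents state no figure for time to ON, so there is none to reproduce. The check has two parts.

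**1. Does any passage close the gap?**

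- SAP 10.8 says the method is the same as for time to response. That carries over Kaplan-Meier. SAP 10.4 states no limit and needs none, because the Day 0 post-dose Part III ratings end at 120 minutes. The ON/OFF ratings go on to 240.
- SAP 8.5.4 applies no assessment windows. SAP 8 admits scheduled data to the tables, and 240 minutes is a scheduled time.
- The endpoint definitions (Protocol synopsis and 3.2; SAP 3.2.2) give no limit for time to ON.

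None does.

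**2. When does a reported quartile change?**

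Inputs:

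- Active groups have 6 subjects each (Cohort 4 up to 9).
- Pooled placebo is 2 + 2 + 2 + 2 = 8, or 9 if Cohort 4 is expanded.
- At the interim analysis of Cohorts 1 and 2, pooled placebo is 2 + 2 = 4.

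Assumptions: no missing ratings, and quartile *p* is the first time at which S(t) ≤ 1 − *p* (the SAP names no rule).

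Let *k* of *n* subjects be ON by the 120-minute rating and *m* of the other *n* − *k* be first ON at 240.

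- As written, S(240) = 1 − (*k* + *m*)/*n*.
- With the others censored at 120, the curve stays at 1 − *k*/*n*.
- Quartile *p* needs ceil(*np*) subjects ON. It is exposed when *k* < ceil(*np*), and it is reported as about 240 minutes once *m* ≥ ceil(*np*) − *k*.

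| n | Needed ON: 25th / median / 75th | Largest k still exposed: 25th / median / 75th |
|---|---|---|
| 4 (interim placebo) | 1 / 2 / 3 | 0 / 1 / 2 |
| 6 (active) | 2 / 3 / 5 | 1 / 2 / 4 |
| 8 (pooled placebo) | 2 / 4 / 6 | 1 / 3 / 5 |
| 9 (expanded Cohort 4 active, or pooled placebo) | 3 / 5 / 7 | 2 / 4 / 6 |

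At each limit one further ON at 240 is enough. With fewer ON by 120, more are needed:

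- **Placebo, n = 8, k = 1.** The median needs 4 − 1 = 3 of the remaining 7 and the 75th percentile needs 6 − 1 = 5 of 7. As written, cumulative ON at 240 minutes runs from 1/8 = 12.5% (*m* = 0) to 8/8 = 100% (*m* = 7). Censored at 120, it stays at 12.5% and no quartile is reached.
- **Active, n = 6, k = 3.** The median is unchanged. The 75th percentile needs 5 − 3 = 2 of the remaining 3. Censored at 120, cumulative ON stays at 3/6 = 50% and the 75th percentile is not reached.

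Under the strict rule S(t) < 1 − *p*, the largest exposed *k* for *n* = 4, 6, 8 and 9 becomes 2, 3, 4 and 4 for the median, and 3, 4, 6 and 6 for the 75th percentile.

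**Confidence limits can also change when the quartile does not.** Take *n* = 8 with 5 ON at 60 minutes, and assume log-log limits (the SAP names no method).

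- At 60 minutes S = 3/8 and the Greenwood sum is 5/(8 × 3) = 0.208. The upper 95% limit for S is 0.67. This is above 0.5, so the upper limit of the median is not reached.
- If 2 of the other 3 are ON at 240, S = 1/8 and the sum is 0.208 + 2/(3 × 1) = 0.875. The upper limit for S is 0.42, so the upper limit of the median becomes 240 minutes. The median itself is 60 minutes either way.

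**The case against.** The case against rests on weight more than on text.

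- **Exploratory endpoint.** SAP 3.3 and 3.4 set no formal hypotheses, SAP 10 calls these analyses exploratory, and time to ON is the last motor endpoint listed. No planned test, dose decision or stopping rule uses it. This stands, and it limits the harm to interpretation.
- **The data to spot the problem are reported.** ON/OFF status, time to ON and medication intake are listed by subject, and the plot would show a step near 240 minutes. This stands for a reader who knows the schedule. The summary table would still print the value as a time to ON for the randomised group.
- **A 120-minute horizon may have been intended.** The reference to the time-to-response method makes that plausible, but it states no cutoff. A programmer following SAP 10.8 exactly would include 240 minutes.
- **The contrast with duration of response is weak.** Part III ratings end at 120 minutes anyway, so the limit in Protocol 12.5 largely restates the schedule. This is fair. The concern does not depend on the contrast.
- **The interim table may be restricted.** The time-to-ON summary is flagged for the interim analysis, but SAP 5.1 lets the unblinded statistician withhold statistics that identify individuals. With 4 placebo subjects, quartiles might well be withheld. This also stands.
- **No ON rate is assumed.** The counts show when a quartile is exposed, not how likely that is. The documents give no rate from which to calculate it.

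**Conclusion.** The concern holds. Followed as written, SAP 10.8 reports an ON first seen after usual Parkinson's medication as time to ON for INP103 or placebo. Curve estimates up to the 120-minute rating are unaffected. The 240-minute step, any quartile not reached by 120 minutes, and some upper confidence limits depend on a rating taken after planned non-study treatment. The median is exposed at up to 2 of 6, 3 of 8 or 4 of 9 ON by 120 minutes, and the 75th percentile at up to 4 of 6, 5 of 8 or 6 of 9. These counts assume complete ratings and the S(t) ≤ 1 − *p* rule. The SAP plans no between-group difference in cumulative ON, so no planned contrast is biased. This should be fixed before the analysis, but it does not threaten the trial's primary safety objective.

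**What to change.** Add one rule to SAP 10.8, applied to both the investigator's and the subject's ratings:

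- Count as events only ON at ratings up to and including the nominal 120-minute rating, at its actual time, and taken before the first post-dose usual or rescue Parkinson's medication.
- Censor every other subject at the last such rating.
- If a medication time is missing, treat the nominal 120-minute rating as the last eligible one, since Protocol 7.4.3 places medication after it.
- Report ON/OFF status at 240 minutes in a separate table.

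The cutoff should follow the nominal rating rather than the clock, because the rating window allows the 120-minute assessment to fall as late as 120 + 10 = 130 minutes. As an optional clarification, SAP 10.4 could say that time to response uses the Day 0 Part III ratings up to the nominal 120-minute time point.

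The cost is this short text and minor programming. SAP 9.5 refers to medication dates and times, so the times appear to be collected, although the case report form is not among the documents. Some percentiles will be reported as not reached. Nothing changes in study conduct, and the 240-minute data are kept.

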11. SAFETY ANALYSES

All safety analyses will be conducted on the Safety population.

Overall, data for adverse events, clinical laboratory assessment, vital signs, ECG and other safety measurements (orthostatic hypotension, dyskinesia assessment, nasal inspection, \mp physical examination, subject questionnaire, domiciled status) will be presented by subject in listings (including assessments of abnormality and clinical significance, where applicable). Summaries will be prepared for key variables (detailed below) by cohort and treatment group and protocol specified time-point (where applicable) for the Safety population.

No inferential statistical testing will be performed for any safety variable.

11.1. Adverse Events

Adverse events will be coded using MedDRA[®] Version 21.0. Adverse events will be grouped by system organ class (SOC) and preferred term (PT) and summarized, by actual treatment at time of onset of the AE. The summary tables will present the frequency and percentage of total subjects and number of events, by SOC and by PT.

For the summaries of AEs, subjects who experience the same AE (in terms of the MedDRA preferred term) more than once will only be counted once for that event in the number of subjects but all occurrences of the same event will be counted in the number of events.

AE summaries will include Treatment Emergent Adverse Events (TEAEs) and AE onset within benserazide period.

- TEAE is defined as AEs which commence on or after the time of first study drug administration (INP103 or placebo) through to the end of the study. AEs without an onset date or time will be defined as treatment emergent except if an incomplete date (e.g., month and year) clearly indicates that the event started prior to start of first study drug administration or if the AE stop date indicates that the event started and/or stopped prior to start of first study drug administration.
- AE onset within benserazide period: AE onset within the benserazide period is defined as the AE onset after the dose of benserazide and before the dose of INP103/ Placebo. AEs without an onset date or time will be defined into this category except if an incomplete date (e.g., month and year) clearly indicates that the event started prior to start of benserazide administration or if the AE stop date indicates that the event started and/or stopped prior to start of benserazide administration.

Incidence of adverse events as well as the duration, severity, relationship to treatment, outcome and actions taken will be listed for each subject. In addition, listings of AEs leading to discontinuation of the study, SAEs and deaths, will be provided if applicable.

‘Treatment Related’ TEAE is defined as any TEAE that is reported as having a *Definite, Probable* or *Possible* relationship to the study drug.

The following AE summaries will be provided:

- Overall summary of TEAEs, including below information
 - Any TEAE
 - AEs onset within Benserazide Period

CONFIDENTIAL AND PROPRIETARY

- Any severe TEAE
 - Any Treatment-related TEAE
 - Any serious TEAE
 - Any TEAE leading to study drug interruption
 - Any TEAE leading to study drug withdrawn
 - Any TEAE leading to discontinuation from study
 - Any Life threatening TEAE
 - Any TEAE leading to death
- Adverse Events onset within Benserazide Period by SOC and PT
 - TEAEs overall and by SOC and PT
 - TEAEs by severity, overall and by SOC and PT
 - Treatment-related TEAEs overall and by SOC and PT
 - Serious TEAEs overall and by SOC and PT

In the summary tables, AEs will be presented by decreasing frequency of total events overall within each SOC and then similarly by decreasing frequency of total events overall within each PT. SOCs or PTs with equal frequencies will be sorted alphabetically.

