Continuous safety data will be summarized with descriptive statistics (arithmetic mean, SD, median, minimum, and maximum) by treatment. Categorical safety data will be summarized with frequency counts and percentages by treatment.

AEs will be coded using the Medical Dictionary for Regulatory Activities (MedDRA®) version 21.0. A by-subject AE data listing, including verbatim term, preferred term, system organ class, treatment, severity, and relationship to INP103 or placebo, will be provided. The number of subjects experiencing treatment emergent AEs (TEAEs) and number of individual TEAEs will be summarized by treatment, system organ class and preferred term. TEAEs will also be summarized by seriousness, severity, relationship to INP103 or placebo and the time of onset relative to dosing.

Dyskinesia assessment, nasal inspection, laboratory evaluations, vital signs assessments (including supine and standing blood pressure, all other vital signs supine only) and ECG parameters will be summarized by treatment and collection time point. A summary of change-from-baseline at each time-

point by treatment will be presented. In addition, the proportion of subjects experiencing orthostatic hypotension or abnormal ECGs will be summarized by treatment group.

Proportion of subjects with abnormal physical examination findings will be summarized by treatment group.

Prior and concomitant medications will be listed by subject and coded using World Health Organization (WHO) drug dictionary, Version MAR-2018 and summarized by therapeutic class (Level 4 for anti-PD medications and Level 2 for other medications) and preferred name.

Medical history will be listed by subject.

Pharmacokinetics:

Reported (i.e. uncorrected) and baseline corrected L-dopa concentrations will be summarized with descriptive statistics (arithmetic and geometric mean, SD, CV% median, minimum, and maximum) by treatment group and time point. In addition, PK parameters ($AUC_{0-0.5h}$, AUC_{0-1h} , AUC_{0-2h} , C_{max} , T_{max}) derived from both reported and baseline corrected L-dopa concentration data will be summarized with descriptive statistics by treatment group.

Exploratory Analysis

- PK profile of carbidopa (Cohort 4 only) for the first 120 minutes following dosing with INP103 will be summarized with the PK parameters of AUC_{0-2h} , C_{max} and T_{max} .

Pharmacodynamics:

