3.2. Study Endpoints

3.2.1. Primary Endpoints

Safety and tolerability, including the assessment of physical examinations (including nasal inspection), electrocardiograms (ECGs), vital signs (including supine and standing blood pressure, all other vital signs supine only), clinical laboratory results, and adverse events (AEs; specifically, overall dyskinesia assessments) over the immediate 240 minutes following dosing and over 7 days of follow-up.

These primary endpoints, specific to the full study analysis, will also be considered the primary endpoints for the interim analysis (reviewed in a blinded manner). The data for the primary endpoints will also be reviewed at each safety monitoring committee meeting in a blinded manner.

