6.7.6. Other Derivations

Body Mass Index (kg/m^2 , to one decimal place) = Body Weight (kg) / (Height^2 (m)).

For any observed original results above the upper limit or below the lower limit in laboratory assessment, the original results will be presented in data listing and the upper limit value or the lower limit value will be used for summary table. For example, *0.1* will be used if the original result is “<0.1”, while *1000* will be used if the original result is “>=1000”.

Treatment emergent adverse events will be defined as AEs which commence on or after the time of start of first study drug administration. AEs without an onset date or time will be defined as treatment emergent except if an incomplete date (e.g., month and year) clearly indicates that the event started prior to start of first study drug administration or if the AE stop date indicates that the event started and/or stopped prior to start of first study drug administration.

Adverse event time since study drug administration (in minutes) = (Onset Date + Onset Time) – (Study Drug Administration Date + Study Drug Administration Time).

Duration of AE (in minutes) = (Resolution Date + Resolution Time) - (Onset Date + Onset Time).

The response is defined as an improvement of $\geq 30\%$ in MDS-UPDRS Part III score from baseline to post INP103/Placebo dosing time point for each patient.

Time to response = (Time at FIRST response [as defined above] post study drug administration [INP103/Placebo] – Time at the first study drug administration [INP103/Placebo] [Unit = minutes]).

The orthostatic hypotension is defined as a reduction in systolic blood pressure of 20 mmHg or more, and/or a reduction in diastolic blood pressure of 10 mmHg or more, for the standing measurement compared to the supine measurement.

All AUC values will be calculated by using the trapezoidal rule.

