| | 14.2.2.1 | Summary of Movement Disorder Society Unified Parkinson's Disease Rating Scale (MDS-UPDRS) Part III Score | ITT | Y | 1 |
| | 14.2.2.2 | MMRM of Movement Disorder Society Unified Parkinson's Disease Rating Scale (MDS-UPDRS) Part III Score | ITT | N | 2 |
| Figure | 14.2.2.3 | Individual Change from Baseline in Movement Disorder Society Unified Parkinson's Disease Rating Scale (MDS-UPDRS) Part III Score | ITT | N | 2 |
| | 14.2.2.4 | Summary of Cumulative Response | ITT | Y | 2 |
| | 14.2.2.5 | Summary of Time-to-Response | ITT | Y | 2 |
| | 14.2.2.6 | Duration of Response | ITT | N | 2 |
| Figure | 14.2.2.7 | Kaplan-Meier Plot for Time-to-Response | ITT | N | 2 |
| | 14.2.2.8 | Summary of AUC of change in Movement Disorder Society Unified Parkinson's Disease Rating Scale (MDS-UPDRS) Part III Score | ITT | N | 2 |

CONFIDENTIAL AND PROPRIETARY

| Header | Table Number | Table Title | Analysis Population | Interim Analysis | Priority |
|--------|--------------|--|---------------------|------------------|----------|
| | 14.2.2.9 | ANCOVA of AUC of change in Movement Disorder Society Unified Parkinson's Disease Rating Scale (MDS-UPDRS) Part III Score | ITT | N | 2 |
| | 14.2.2.10 | Summary of the Maximum Response | ITT | Y | 2 |
| | 14.2.2.11 | ANCOVA of The Maximum Response | ITT | N | 2 |
| | 14.2.2.12 | Summary of Time-to-ON | ITT | Y | 2 |
| Figure | 14.2.2.13 | Kaplan-Meier estimator for Time-to-ON status | ITT | N | 2 |
| | 14.2.3 | Pharmacokinetic versus Pharmacodynamic Relationship | | | |
| Figure | 14.2.3.1 | Time-matched Change from baseline in MDS-UPDRS Part III score versus uncorrected plasma L-Dopa concentrations | ITT | N | 2 |
| 14.3 | | Safety Data Summary Tables | | | |
| | 14.3.1 | Adverse Events | | | |
| | 14.3.1.1 | Overall Summary of Treatment Emergent Adverse Events | Safety | Y | 1 |
| | 14.3.1.2 | Adverse Events onset within Benserazide Period | Benserazide Safety | N | 2 |
| | 14.3.1.3 | Treatment Emergent Adverse Events | Safety | Y | 1 |
| | 14.3.1.4 | Treatment Emergent Adverse Events by Severity | Safety | N | 2 |
| | 14.3.1.5 | Treatment-Related Treatment Emergent Adverse Events | Safety | N | 2 |
| | 14.3.1.6 | Serious Treatment Emergent Adverse Events | Safety | N | 1 |
| | 14.3.2 | Listings of Deaths, Other Serious and Significant Adverse Events | Not Applicable | | |

CONFIDENTIAL AND PROPRIETARY

| Header | Table Number | Table Title | Analysis Population | Interim Analysis | Priority |

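### The SAP promises treatment-emergent AEs by time of onset and derives the variable, but its AE section and table list only pool events from dosing to end of study

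*SAP*

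**What the plan says.** SAP section 3.2.1 (and protocol section 3.1) sets the primary safety and tolerability endpoint "over the immediate 240 minutes following dosing and over 7 days of follow-up". AEs are one component, alongside physical and nasal examination, ECG, vital signs and laboratory results.

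On analysis, the SAP synopsis says: "TEAEs will also be summarized by seriousness, severity, relationship to INP103 or placebo and the time of onset relative to dosing". Protocol section 12.3 makes the same commitment. SAP section 6.7.6 defines the variable needed: minutes from study drug administration to AE onset.

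SAP section 11.1 then defines TEAEs over one interval: "AEs which commence on or after the time of first study drug administration (INP103 or placebo) through to the end of the study". Its list begins "The following AE summaries will be provided" and names an overall summary, AEs arising between benserazide and study drug, TEAEs by system organ class (SOC) and preferred term (PT), "TEAEs by severity, overall and by SOC and PT", treatment-related TEAEs and serious TEAEs. Section 17.2.2 carries these over as tables 14.3.1.1 to 14.3.1.6.

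**The concern.** The endpoint names two windows and the synopsis promises a summary by onset, but the operative AE section and the table list deliver neither. As written, no planned table reports TEAEs in the first 240 minutes, and the derived onset variable feeds no specified summary.

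This matters because the primary objective is a comparison with placebo. Under protocol section 7.4.3, subjects take their regular PD medication at 120 minutes whether or not they are ON, and may take rescue medication if still OFF. Most of the pooled interval therefore follows other dopaminergic dosing in every group. If later events occur at similar rates in all groups, adding them to the early events narrows any acute difference between INP103 and placebo. Groups are small: 6 per active dose (up to 9 in Cohort 4) and 8 to 9 pooled placebo. A few later events can change how the table reads.

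**Working it through.** The plan gives no figure to reproduce on this point. The main check is a comparison of texts, followed by two short calculations.

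**1. The four promised breakdowns against the planned tables**

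| Breakdown promised in the SAP synopsis | Item in SAP 11.1 | Table in SAP 17.2.2 |
|---|---|---|
| Seriousness | Serious TEAEs | 14.3.1.6 |
| Severity | TEAEs by severity | 14.3.1.4, "Treatment Emergent Adverse Events by Severity" |
| Relationship | Treatment-related TEAEs | 14.3.1.5 |
| Time of onset | None | None |

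The other three tables are the overall summary (14.3.1.1), benserazide-period AEs (14.3.1.2) and TEAEs (14.3.1.3). Three of the four promised breakdowns have a table and one does not.

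**2. Is the omission a declared change?** Protocol section 12 lets the SAP supersede the protocol. That does not explain the gap, because the SAP's own synopsis keeps the commitment. Where the SAP does depart from the protocol, as for the ITT population in section 6.5.2, it says so. Nothing of the kind appears for AE onset.

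**3. Does the general safety wording fill the gap?** SAP section 11 says "Summaries will be prepared for key variables (detailed below) by cohort and treatment group and protocol specified time-point (where applicable) for the Safety population". AEs are collected continuously, not at scheduled time points, and section 11.1, which supplies the detail, contains no onset split.

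**4. Share of the pooled interval.** Inputs are 240 minutes (SAP 3.2.1), 120 minutes (protocol 7.4.3), and end of study at Day 7, with +2 days or exceptionally +4 days (protocol 7.5).

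- 7 days = 7 × 1,440 = 10,080 minutes: 240/10,080 = 2.4%; 120/10,080 = 1.2%
- 9 days = 12,960 minutes: 240/12,960 = 1.9%
- 11 days = 15,840 minutes: 240/15,840 = 1.5%

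These are shares of clock time, not of events.

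**5. Dilution, under assumed rates.** Let a and p be the risks of an early event on active and placebo, and b a later background risk that is common to both and independent of early events. The pooled risk is 1 − (1 − a)(1 − b) on active, and likewise with p on placebo, so the pooled difference is (a − p)(1 − b). The documents give none of these rates. Take a = 30% and p = 5% as assumptions:

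| b | Active, pooled | Placebo, pooled | Difference |
|---|---|---|---|
| 0% | 30% | 5% | 25 points |
| 20% | 1 − 0.70 × 0.80 = 44% | 1 − 0.95 × 0.80 = 24% | 20 points |
| 40% | 1 − 0.70 × 0.60 = 58% | 1 − 0.95 × 0.60 = 43% | 15 points |

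**The case against.** The strongest reply is that little is lost. The endpoint is composite, and SAP sections 11.4 to 11.7 already summarise laboratory results, vital signs, ECG, dyskinesia grade, nasal findings, orthostatic hypotension and new physical findings by collection time point. The endpoint text singles out dyskinesia within the AE item, and dyskinesia is rated up to 240 minutes and again at follow-up. AEs are also listed by subject (Listing 16.2.7.1), so early events can be traced among 32 to 36 subjects. Relationship grading already weighs timing and concomitant therapy. Safety is descriptive, so no test result is affected.

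All of that stands, and it limits the point to the general AE tables. It does not remove it: a listing is not the promised summary, and investigator attribution is not onset time.

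A reader might infer more than the documents support:

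- That the 240-minute window is lost for the whole primary endpoint. It is not; the other components keep their time points.
- That later events mostly reflect usual treatment and swamp the comparison, so that only the first 120 minutes are informative. No AE rates are given, clock-time shares say nothing about event counts, and nothing shows that INP103 effects end at 120 minutes.
- That the documents require an AE cut at 120 minutes. They name 240 minutes and 7 days only.

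**Conclusion.** The point holds as an internal inconsistency in the SAP. The endpoint definition, the synopsis and the derived variable all point to a summary of TEAEs by onset; section 11.1 and tables 14.3.1.1 to 14.3.1.6 omit it without a declared change. This part is textual and needs no assumption.

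The consequence is possible dilution of an acute difference. Its size cannot be fixed from the documents. In the worked example the difference falls by a proportion equal to the background risk, from no loss at 0% to two fifths at 40%. That rests on assumed early rates, a background risk equal across groups, and independence of early and later events. It shows attenuation, not a reversal. The change should be made because the table completes a planned summary of a primary endpoint component; it does not put the safety analysis as a whole in doubt.

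**What to change.** Add one TEAE table to SAP sections 11.1 and 17.2.2, using the onset variable from section 6.7.6: overall and by SOC and PT, by treatment group, with columns for 0 to 240 minutes and for over 240 minutes to end of study. Keep the existing whole-period table beside it.

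State which window a TEAE with a missing onset time enters. Section 11.1 makes such events treatment-emergent by default but assigns no window.

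Optionally, add a cut at each subject's actual time of first usual or rescue PD medication. A fixed 120 minutes would not do this, because protocol section 7.4.3 has that medication given after the 120-minute assessments are complete. Add a footnote that subject counts do not sum across windows, since one subject can have events in several.

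The cost is one extra descriptive table from an existing variable. Its cells will be sparse at this sample size.
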